### 5.2.3 Exploratory Endpoints

Exploratory endpoints will be assessed through the following parameters in healthy subjects after dosing on Day 1:

#### 6.0 TRIAL DESIGN AND DESCRIPTION

### 6.1 Trial Design

This is an FIH, randomized, double-blind, placebo-controlled trial to evaluate the safety, tolerability, and PK of TAK-418 in healthy adult subjects. The trial will also explore the PD of TAK-418 and its effects on selected biomarkers following single oral doses in healthy adult subjects.

TAK-418 will be administered orally as a capsule formulation. TAK-418 and placebo will be prepared and dispensed in a blinded fashion by an unblinded pharmacist or qualified trial site personnel. The subject, the investigator, and sponsor personnel or delegate(s) who are involved in the treatment or clinical evaluation of the subjects will be unaware of the treatment group assignments.

Because this is a phase 1 assessment of TAK-418 in humans, and the PK, PD, and safety profiles of the compound are still being evaluated, modifications to the dose or dosing regimen may be required to achieve the scientific goals of the trial objectives and/or to ensure appropriate safety monitoring of the trial subjects. Details of allowed modifications are provided in Section 6.4.

This study consists of 5 cohorts of subjects, sequentially paneled, with a double-blind design. Each cohort will consist of 8 subjects, where 6 subjects will be randomized to receive TAK-418 and 2 subjects will be assigned to receive matching placebo. A minimum of 4 male subjects will be enrolled in each cohort. The trial population will be approximately 40 healthy subjects. Additional cohorts may be studied if deemed necessary to fully characterize the pharmacologically active exposure range. For Cohort 3, there will be at least 7 days of washout between dose administration in the fasted and fed states.

The planned dose levels of TAK-418 to be evaluated in Cohorts 1 to 5 are outlined in Table 6.a.

Table 6.a Schematic and Planned Doses of Trial Design—Cohorts 1 to 5

Dose 5 mg	Dose 15 mg	Dose 45 mg	Dose 90 mg	Dose 180 mg
Cohort 1	Cohort 2	Cohort 3A and 3B	Cohort 4	Cohort 5
(n=8; 6 active: 2 placebo)				

Additional cohorts may be studied if deemed necessary to fully characterize the pharmacologically active exposure range.

### CCI

A sentinel dosing regimen will be used for Cohort 1 (with the initial 2 subjects [1a] receiving either active drug or placebo in a 1:1 ratio) to ensure adequate safety and tolerability. After a minimum of 72 hours after the dosing of Cohort 1a, 3 subjects (Cohort 1b) will be dosed after review of the postdose safety and tolerability of the initial 2 subjects (Cohort 1a). After a minimum of 72 hours after dosing Cohort1b, the last 3 subjects of Cohort 1(1c), will be dosed after review of the postdose safety and tolerability.

A staggered dosing regimen will be used for Cohorts 2 to 5. Each cohort will be divided by 2 groups (3 active: 1 placebo), and the second group will be dosed after a minimum of 48 hours after the first group, following assessment of safety and tolerability data. Subjects in Cohort 3 receive 2 doses (fasted and fed state). There will be at least 7 days of washout between dose administrations.

The trial schedule is detailed in Table 6.b.

Ta	h	le	6.	h	Trial	Sc	hedule
14		10	v	• •	11141		IICUUIC

Screening	Pretreatment	Treat			
Period	(a)	Dose Administration (b)	Postdose Procedures (b)	Posttrial (c)	
Days -28 to -2	Day -1	Day 1	Days 1 to 4	Day 14 (±2) (c)	
				Days 91, 93, 182, and 184 (±7)	

(a) CCI
(b) Subjects will remain in the phase 1 unit for a minimum of 48 hours following the dose of trial drug and may be released after 48 hours and complete the 72 hour and later procedures at an outpatient visit. Subjects may be kept in the clinic for longer time at PI's discretion.

(c) CCI

#### **6.2** Dose Escalation

Dose escalation and subsequent dose levels will be based on a blinded review of available safety (including neurological assessment) and tolerability data from the previous dose levels and will only occur following agreement between the investigator and the sponsor. PK data will be used to guide dose selection after each cohort.

Following Cohort 1, subsequent dose levels may be higher, may be lower, or may remain the same as the preceding dose level. After Cohort 2, dose escalations will be limited to an escalated dose that is predicted to give no greater than a 3-fold increase in either  $C_{max}$  or AUC of the immediate prior dose level. Dosing will continue as long as the mean AUC of the highest dose level is predicted not to exceed the mean area under the serum concentration-time curve from time 0 to 24 hours (AUC24) at the no effect level for  $^{CCI}$ findings in male monkeys (the more sensitive species) from the 13-week toxicology study (CCI ) or the mean  $C_{max}$  of the highest dose is predicted not to exceed one-tenth of the mean  $C_{max}$  of the NOAEL from the 4 weeks toxicology study in monkeys (CCI ). If needed, a higher dose than the planned dose of 180 mg but less than 300 mg will be evaluated providing that the predicted exposure of this dose does not exceed the exposure levels mentioned above. If the majority of plasma concentrations of TAK-418F are below the limit of detection, the dose will be escalated to the next planned dose level provided safety and tolerability at the preceding dose level are considered acceptable.

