#### **Trial Design:**

This first-in-human (FIH), randomized, double-blind, placebo-controlled trial is designed to evaluate the safety, tolerability, and pharmacokinetics (PK) of TAK-418 in healthy adult subjects.

TAK-418 and placebo will be administered orally in capsule formulation and will be prepared and dispensed in a blinded fashion by an unblinded pharmacist or qualified trial site personnel; the subject, the investigator, and the sponsor personnel or delegate(s) who are involved in the treatment or clinical evaluation of the subjects will be unaware of the treatment group assignments.

Since the PK, pharmacodynamic, and safety profiles of TAK-418 in humans are still being evaluated, modifications to the dose or dosing regimen may be required to achieve the scientific goals of the trial objectives and/or to ensure appropriate safety monitoring of the trial subjects. Dose escalation and subsequent dose levels will be based on a blinded review of available safety (including neurological assessment), tolerability, and PK data from the previous dose levels and will only occur following agreement between the investigator and the sponsor.

This study will involve 40 subjects, equally divided among 5 sequential cohorts of 8 subjects each, as shown in Table 1. In each cohort, 6 subjects will be randomized to receive TAK-418 and 2 will receive matching placebo. A minimum of 4 male subjects will be enrolled in each cohort. The schedule for dosing and procedures is provided in Table 2.

Table 1. Schematic and Planned Doses for Cohorts 1 Through 5

Dose 5 mg	Dose 15 mg	Dose 45 mg	Dose 90 mg	Dose 180 mg
Cohort 1	Cohort 2	Cohort 3A and 3B	Cohort 4	Cohort 5
(n=8; 6 active: 2 placebo)	(n=8; 6 active: 2 placebo)	(n=8; 6 active: 2 placebo)	(n=8; 6 active: 2 placebo)	(n=8; 6 active: 2 placebo)

Additional cohorts may be studied if deemed necessary to fully characterize the pharmacologically active exposure range.

Doses planned to be administered range from 5 to 180 mg, but the actual doses administered after the first dose will be based on emerging safety and tolerability data from the previous doses. If needed, a dose higher than 180 mg but less than 300 mg may be evaluated providing its predicted exposure does not exceed the following exposure levels: the highest dose administered will have a predicted mean area under the plasma concentration-time curve (AUC) that does not exceed the monkey AUC at the no effect level for the following exposure levels:

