the 13-week toxicology study or mean maximum observed concentration ( $C_{max}$ ) that does not exceed one-tenth ( $C_{max}$ ) of the monkey  $C_{max}$  at the NOAEL ( $C_{max}$ ) from the 4-week toxicology study.

Because this is a FIH trial, a sentinel dosing regimen will be used for Cohort 1 (with the initial 2 subjects receiving either active drug or placebo [1:1]) to ensure adequate safety and tolerability. The remaining 6 subjects will be dosed in 2 groups of 3 subjects each after a review of 72 hours postdose safety and tolerability data of the previous group. A staggered dosing regimen will be used for Cohorts 2 to 5. Each cohort will be divided by 2 groups (3 active:1 placebo), and the second group will be dosed 48 hours after the first group, following assessment of safety and tolerability data. Subjects in Cohort 3 will receive 2 doses (under fasted state [Cohort 3A] and with food [Cohort 3B]), with at least 7

days of washout between dose administrations. Subjects enrolled in Cohort 3A will return to the site to complete Cohort 3B and will be administered TAK-418/placebo under fed condition with a high fat/high calorie breakfast, which must be consumed within 30 minutes and the dose given within 5 minutes after the end of the meal. All assessments from Day -1 to Day 4 in Cohort 3B will be same as in Cohort 3A and there will be no Day 14 follow-up for Cohort 3A. Post-trial assessments days will be adjusted (including follow-up on Day 14 for all subjects and Days 91, 93, and 182 and 184 postdose, if needed) with respect to Cohort 3B.

Table 2. Trial Schedule

	Pretreatment	Trea	tment	
Screening Period (a)	(a)	Dose Administration (b)	Postdose Procedures (b)	Post-trial (c)
Days -28 to -2	Day -1	Day 1	Days 1 to 4	Day 14 (±2) Days 91, 93, 182, and 184 (±7)

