#### **Secondary Objective:**

The secondary objective of this trial is to evaluate the PK of TAK-418 free base (F) following a single oral doses (under fasted and fed states) in healthy subjects.

Subject Population: Healthy adults aged 18 to 55 years,	inclusive.								
Number of Subjects:	Number of Sites:								
40 subjects (8 subjects in each of 5 cohorts)	1 site								
Dose Levels:	Route of Administration:								
5 mg (Cohort 1), 15 mg (Cohort 2), 45 mg (Cohort 3), 90 mg (Cohort 4), and 180 mg (Cohort 5)	Oral								
Duration of Treatment:	Period of Evaluation:								
One single dose in Cohorts 1, 2, 4, and 5 Two single doses in Cohort 3 (under fasted and fed	Female subjects (Cohorts 1, 2, 4, and 5): approximately 42 days.								
states)	Female subjects (Cohort 3): approximately 49 days.								
	Male subjects (Cohorts 1, 2, 4, and 5): approximately 121 days (212 days if serum analysis is abnormal on Day 93).								
	Male subjects (Cohort 3): approximately 128 days (219 days if serum analysis is abnormal on Day 93 post Cohort 3B).								

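### The AUC and Cmax ceilings that limit dose escalation are joined by *or*, so read literally dosing may continue when one of them is predicted to be exceeded

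*Protocol*

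**What the plan says.** Protocol 6.2 states the continuation rule in one sentence with two limbs. The first reads "Dosing will continue as long as the mean AUC of the highest dose level is predicted not to exceed" the monkey AUC24 at a no effect level in males, "from the 13-week toxicology study (CCI ) or the mean" Cmax "of the highest dose is predicted not to exceed one-tenth of the mean" Cmax at the NOAEL in the 4-week monkey study (the CCI mark is the document's own redaction). The numerical limits are blacked out.

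The synopsis, Protocol 6.1 and SAP 4.4 restate the limits as a property of the highest dose administered, with the same connective. The synopsis, for example, has "the 13-week toxicology study or mean maximum observed concentration" followed by the Cmax limit.

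Two nearby sentences bear on intent:

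- A dose above 180 mg and below 300 mg may be given in 6.2 if "the predicted exposure of this dose does not exceed the exposure levels mentioned above", and in the synopsis "providing its predicted exposure does not exceed the following exposure levels". Protocol 6.1 and SAP 4.4 carry the same condition. The noun is plural throughout.
- After Cohort 2, each escalation must be "predicted to give no greater than a 3-fold increase in either" Cmax or AUC relative to the dose before.

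The Cmax limit is not worded alike everywhere. Protocol 6.2 and the synopsis tie it to the NOAEL. Protocol 6.1 and SAP 4.4 refer only to the monkey Cmax from the 4-week study.

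**The concern.** A ceiling on predicted exposure is a stated stopping rule in healthy volunteers who can expect no clinical benefit (Protocol 4.3). A person applying it should not have to infer whether one limit or both must hold.

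The two ceilings are not substitutes. They use different exposure measures, come from different studies, and only the Cmax limit carries a tenfold margin. Meeting one does not show that the other is met. Total and peak exposure can also move separately, for instance under the high-fat meal of Cohort 3B; that is my inference, not a statement in the documents.

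The missing reference to the NOAEL adds a smaller uncertainty. Protocol 6.3.2 shows that the 4-week monkey study included a dose with adverse findings (100 mg/kg/day) as well as the NOAEL dose, so a limit based on the study's Cmax, with no dose level named, does not identify one value.

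**Working it through.** No figure in the plan is at issue, so the check is on wording and logic.

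**1. Grammar of the rule.** A phrase such as *not to exceed A or B* can mean *neither*, because one negation covers both items. The 3-fold rule works that way: one limit on the increase, applied to either measure. The ceiling sentence in 6.2 is built differently. Each limb has its own subject, verb and negation, and the whole hangs on a permissive opening. That makes the limbs alternative sufficient conditions. The synopsis, 6.1 and SAP 4.4 also repeat the negation in each limb.

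**2. What the two connectives permit.** For a candidate dose there are four predicted states:

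| Mean AUC | Mean Cmax | *or* (as written) | *and* |
|---|---|---|---|
| within | within | continue | continue |
| within | exceeded | continue | stop |
| exceeded | within | continue | stop |
| exceeded | exceeded | stop | stop |

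As written, dosing continues in 3 of 4 states; with *and*, in 1 of 4. The rules differ in exactly the two states where one ceiling is predicted to be exceeded. The count describes the logic and says nothing about how likely each state is.

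**3. What the difference would be in dose.** Let D_A and D_C be the doses at which predicted mean AUC and mean Cmax reach their ceilings, and assume that predicted exposure rises with dose. Then:

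- with *and*, the highest permitted dose is min(D_A, D_C);
- with *or*, it is max(D_A, D_C), subject to the separate bound of 300 mg.

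The readings coincide if D_A = D_C, or if both lie above every dose considered. Neither D_A nor D_C can be found, because the ceilings (6.2) and the projected human exposures (6.3.2) are redacted.

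**4. Whether other visible text settles it.**

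- The 3-fold rule limits each step relative to the previous dose. It does not cap absolute exposure.
- Protocol 6.4 forbids exceeding the outlined maximum dose or exposure, but refers to 6.3.2, whose visible text does not say that both ceilings bind.
- Protocol 11.2 requires safety and PK review before each escalation, without stating how the ceilings combine.
- The plural *exposure levels* favours the reading that both apply, but no visible sentence says so.

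**The case against.** The strongest reply is that context already answers the question. The condition for higher doses speaks of exposure levels in the plural, and the adjacent 3-fold rule uses *either … or* for limits that plainly both apply. On that view this is a wording tidy-up. The point about intent stands, and it is why the finding is not put more strongly. It does not remove the need for the edit, because the literal sentence still permits what the authors probably meant to forbid.

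Three further points on the other side also stand:

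- **Missing text.** Appendix E places the main change for the 13-week toxicology data in Section 4.3 and gives management of potential risk as part of the reason, yet only two general sentences of 4.3 are visible. Text that settles the matter may have been removed. The statement that nothing requires both limits is therefore confined to unredacted text.
- **Materiality.** Users of the unredacted protocol can compare the projected exposures with both ceilings. If all planned doses are predicted to fall below both, the two readings agree at those doses.
- **Safeguards.** Blinded safety review, investigator–sponsor agreement and use of PK data for dose selection (6.2), and safety and PK review before escalation (11.2), apply on either reading. They are judgement steps and do not replace a fixed limit.

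A reader might infer that the gap is confined to doses up to 180 mg, since the plural wording governs higher doses. The documents do not support that. The synopsis, 6.1 and SAP 4.4 apply the limits to the highest dose administered without a threshold, and in 6.2 the sentence on higher doses refers back to the same two limits. If the plural resolves the ambiguity, it does so at every dose; if it does not, the ambiguity extends above 180 mg too.

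**Conclusion.** The wording should be corrected. In four places the AUC and Cmax ceilings are joined so that, read literally, dosing may continue with one ceiling predicted to be exceeded, and no unredacted passage states that both must hold. Context suggests that both were intended. The practical size is unknown and cannot be bounded from the visible text.

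Two stronger conclusions are tempting and unsupported:

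- **That the sponsor meant one ceiling to suffice.** The plural noun and the neighbouring 3-fold rule point the other way.
- **That a planned dose would cross a ceiling.** Protocol 6.3.2 converts the 13-week male-monkey NOAEL to a human dose of 77 mg/day, and the protocol's two highest planned doses are above it: 90/77 = 1.2 and 180/77 = 2.3. But this is a body-surface-area dose conversion, not a predicted exposure, and the ceilings are set on exposure. SAP Table 4.a, moreover, tops out at 60 mg (60/77 = 0.8).

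The conclusion rests on the literal grammar of the sentences and on the assumption that no removed text states the combined rule.

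**What to change.** - **Protocol 6.2:** make the sentence restrictive by inserting *only* before *as long as*; replace the *or* between the two limits with *and*, leaving each limit as now written; and end with: a dose predicted to exceed either limit will not be given. This closing clause keeps the present boundary, so a prediction equal to a limit remains allowed. A clause that stopped escalation once a limit was reached would change it.
- **Synopsis, Protocol 6.1 and SAP 4.4:** change the same *or* to *and*.
- **Protocol 6.1 and SAP 4.4:** insert *at the NOAEL* after *monkey Cmax*, to match 6.2 and the synopsis.

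The protocol text governs dosing; the SAP edit only keeps the restatement consistent. The cost is a wording change carried in an amendment, with the IRB/IEC approval of changes that Appendix A requires. It adds no data, procedures or limits. If both ceilings were always meant to bind, it changes nothing about the intended conduct of the trial.

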### 6.3 Justification for Trial Design, Dose, and Endpoints

#### 6.3.1 Justification of Trial Design and Regimen

Because this is an FIH trial, a sentinel dosing regimen will be used for Cohort 1 (with the initial 2 subjects receiving either active drug or placebo [1:1]) to ensure adequate safety and tolerability. The remaining 6 subjects will be dosed in 2 groups of 3 subjects each after a review of 72 hours postdose safety and tolerability data of the previous group. A staggered dosing regimen will be used for Cohorts 2 to 5. Each cohort will be divided by 2 groups (3 active: 1 placebo), and the

second group will be dosed 48 hours after the first group, following assessment of safety and tolerability data. Subjects in Cohort 3 receive 2 doses (fasted and fed state) with food, with at least 7 days of washout between dose administrations.

The planned initial dose of TAK-418 for Cohort 1 is 5 mg. Doses for subsequent periods/cohorts will be determined based on the available safety, tolerability, and PK data from the preceding period/cohort. The doses will be administered to the subjects by the investigator or the investigator's designee. TAK-418 will be administered orally in a capsule formulation.

#### **6.3.2** Dose

The proposed starting dose for this study was determined by calculating the human equivalent dose (HED) (Food and Drug Administration [FDA] Guidance for Industry Estimating the Maximum Safe Starting Dose in Initial Clinical Trials for Therapeutics in Adult Healthy Volunteers, July 2005) from nonclinical toxicity studies and by taking into consideration the estimated pharmacologically active dose (PAD)/exposures in human subjects. Converting the NOAEL of CC for male monkeys from the 13-week toxicity study, which is the more sensitive species, results in a HED value of CCI based on body surface area. Multiplying this HED of CC , a conservative estimate of human body weight, achieves a total daily dose of 77 mg/day. By adding a 10-fold safety factor as per FDA guidance, the maximum recommended starting dose is CCI . The pharmacologically active exposure based on the nonclinical pharmacology models was CCI . Using the most conservative exposure for allometry and physiologically based PK modeling, this exposure would be achieved at a dose of approximately 13 to 35 mg in humans. Therefore, the proposed starting dose is 5 mg, which is below the maximum safe starting dose and projected PAD. In the event that the majority of individual plasma concentrations of TAK-418F in human volunteers are below the limit of detection, the dose will be escalated to the next planned dose level, provided that safety and tolerability at the preceding dose level are considered acceptable.

Convulsions were observed in 3 monkeys at dose levels ≥75 mg/kg/day in the 13-week toxicology study currently in the reporting phase, but were not observed when the dose was lowered to Based on allometric scaling from rat and monkey PK, the projected human TAK-418F Cmax and AUC following a single dose of TAK-418 range from and CCI respectively. The projected human TAK-418F Cmax and AUC following a single dose of TAK-418 180 mg range from L and CCI respectively.

TAK-418 demonstrated good absorption with bioavailability of CCI after oral administration. The terminal disposition phase half-life (t1/2z) value after intravenous (IV) administration was CCI in mice, rats, monkeys, and humans CCI

The in vitro metabolism of [C]TAK-418 was evaluated using hepatic microsomes and hepatic cytosol from mice, rats, dogs, monkeys, and humans. TAK-418 was mainly metabolized to unidentified metabolites via cytochrome P450 (CYP) 2D6 and to a lesser extent via CYP1A2, CYP2C8, CYP2C19, and CYP3A4. In addition, TAK-418 was eliminated via non-CYP pathways (including degradation). TAK-418 has no substantial inhibition of any CYP isoforms (CYP1A2, CYP2B6, CYP2C8, CYP2C9, CYP2C19, CYP2D6, and CYP3A4/5) at concentrations up to 100 μmol/L. An in vitro induction study indicated that TAK-418 has no substantial induction potential for CYP1A2, CYP2B6, or CYP3A4 at concentrations up to 100 μmol/L.

A comprehensive series of nonclinical safety studies (Good Laboratory Practice [GLP] compliant) have been conducted with TAK-418 to support early human studies. No safety concerns were identified in standard safety pharmacology assessment of the central nervous system in rats up to oral doses of 300 mg/kg. An effect on human ether-à-go-go-related gene potassium currents was observed at  $\geq$ 5 µg/mL free concentration of TAK-418 column total plasma concentration of TAK-418 in humans); however, no effect on ECG parameters in telemetrized monkeys was observed through 100 mg/kg although an increase in mean systolic blood pressure (SBP) and diastolic blood pressure (DBP) and an increase in HR were observed at 100 mg/kg; all parameters were normal at 20 mg/kg. A decrease in respiration rate and minute volume at 300 mg/kg but not 100 mg/kg was observed in a rat respiration study using plethysmography.

In GLP-compliant toxicity studies, no safety concerns for genotoxicity were identified in an Ames test or in vivo assessment of DNA damage or micronucleus formation in rats through a 300 mg/kg/day dose. Ultraviolet-visible absorption of light by TAK-418 did not indicate a potential for phototoxicity. In 4-week repeated-dosing toxicity studies in rats, changes that were seen included excessive salivation, decreases in red blood cell parameters, plasma potassium and chloride, increases in urea nitrogen and urine volume, and gastric erosion at 300 mg/kg/day; the for both sexes. The mean  $C_{max}$  and  $AUC_{24}$  values at NOAEL was CCI after the 30th dose were CCI and (females), respectively. In a 4-week monkey toxicity study, decreased food intake, weight loss, and emesis at 100 mg/kg/day were the basis for a NOAEL of CCI The mean Cmax and AUC24 values at CCI after the 28th dose were and (females), respectively. Recovery groups were not included in the 4-week repeat-dose studies. In the 13-week study, currently in the reporting phase, clinical observations associated with administration of TAK-418 included convulsions, emesis, decreased activity, hunched posture, lying on side in cage, and reduced appetite predominantly at 100/75/60 mg/kg/day. degeneration in mature male monkeys was observed in 1 monkey at 20 mg/kg/day and 2 monkeys at 100 mg/kg/day, one of which was recovery. Though severity of finding was less in the one recovery animal, the recovery period was of insufficient duration to assess reversibility. The finding in male monkeys was CCI . Convulsions were observed at NOAEL for **CC** and were observed within 1-hour postdose, lasted less than 2 minutes, and reversed without therapeutic intervention. No convulsions occurred at CCI . Liquid feces occurred

at CCI but did i	not increase in frequence	ey with dose. Minimal d	lecrease in red blood cell
(RBC) mass was observe	ed at 100/75/60 mg/kg/c	day. Minimal increase in	n fibrinogen, decrease in
		ncertain relationship to	TAK-418 was observed in
individual animals across	s dose groups. At CCI	, the mean $C_{max}$	and AUC 24 values after
the 91 st dose were CCI		(males) and CCI	and
CCI (female	s). At CCI, the	mean C max and AUC 24	values after the 91st dose
were CCI	for male m	onkeys.	

